5 STUDY OBJECTIVES AND PURPOSE

The GBCA observational study, will prospectively collect data on the pattern of use for GBCA in real-life diagnostic settings with special reference to Clariscan after its commercial launch in Europe.

The primary and secondary objectives of the study are as follows:

5.1 Primary Objective:

To understand the pattern of use of GBCAs in MRI centres in Europe.

5.2 Secondary Objective:

To assess the effectiveness and safety profile of GBCAs, including Clariscan, in real-life settings.

6 STUDY DESIGN

6.1 Overall Study Design and Plan

A cross-sectional, multicentre (17 European Union [EU] centres), observational study with prospective data collection in patients undergoing contrast-enhanced MR (CE-MR) examination as part of routine clinical practice. Patients will be invited to participate in the study only after the decision has been made by the physician to use contrast agents and Clariscan is already included in the formulary of the hospital/institution as an independent decision prior to investigator taking part in this study. Patients enrolled in the study will not be actively followed up to collect adverse events (AEs) or outcomes. Any spontaneously reported AEs/information will be recorded/reported by the investigators up to 7 days after the MR procedure.

Enrolment

Patients: patients will only be approached to participate in the study after the physician has decided to use GBCA as part of routine clinical practice. Only patients who provide consent (directly or via a person with legal responsibility) will then be included in the study. To enable an understanding of the benefit of GBCAs use in a real world clinical setting the study plan to capture information in a maximum of 5,400 consecutive patients after the study centre has accepted to use Clariscan as an independent decision.

Recruitment will be based on **time (maximum 3 months – a month is equal to 30 calendar days) with a cap of a maximum number of cases per centre by country as defined in Table 1**. It will include all consecutive patients from the start of study after the Clariscan is on formulary of the study centre and available for routine clinical use. The decision to use GBCAs in the study centre/investigator will be made independent of the study after the centre has included Clariscan in the hospital/institution formulary.

The first 25 consecutive patients for which Clariscan is used and the first 25 consecutive patients for which any other GBCAs (all together 25 patients) is used, the images will be transferred for storage to allow a blinded image to read by an expert MR radiology panel to be performed in a future analysis. If the recruitment is less than 25 for either group, then the total images done for the group (Clariscan or GBCAs) during the recruitment period will be transferred. If a patient has repeat imaging for technical reasons and the image is not readable and has been repeated for same indication/reason, then the second readable image will be transferred for storage and analysis.

Investigator: the MR Radiologist; one investigator per centre.

Where a radiology team has multiple physicians involved in the patients' diagnosis and contrast media selections, the site investigators should appoint a single overarching Principal Investigator of the Centre.

Alternatively the study can be focused on a specific patient group under the responsibility of a single physician, as most appropriate to the local circumstances. Cumulative information

collected for the investigator at the end of the study refers to his/her practice during the recruitment period of the study (date of first patient and date of last patient recruitment).

Centre: the institution, hospital or private centre where the study investigator is practicing during the study and patients are recruited for the study from the centre. Cumulative data will be recorded on the eCRF for this centre for the period of recruitment (date of first patient and date of last patient recruitment).

[figure not shown]
Centres with electronic medical record (EMR), picture archiving and communication system (PACS), or any other system in place to collect the cumulative data at the end of the study and compatible for image transfer.

Table 1 Maximum Number of Patients Per Country

Country	Number of Centres	Maximum Number of Patients Allocated to Centres
Norway	1	200
Germany	2	300 + 600 = 900
Spain	3	500 x 2 + 200 = 1200
Italy	3	500 + 400 + 100 = 1000
Portugal	1	300
Poland	1	300 x 3 = 900
France	1	250

An overview of study procedures is presented in [Figure 1](#).

Figure 1 Study Diagram

6.2 Study Rationale

GBCAs are essential to enhanced the images in MR examinations. Over the course of time GBCAs have faced challenges and controversies. It is essential to understand how clinicians use GBCAs in clinical practice including the referral pattern, why enhance, how to select a contract agents, what attributes are important for clinicians in the decision-making process and understanding the process and practice in the real world.

The primary objective of the GBCA observational study, will be to prospectively collect data on the pattern of use for GBCA in real-life setting with special reference to Clariscan after its commercial launch in Europe. The data will be collected for CE-MR procedure and patients in detail to understand the clinical practice. To completely understand the overall picture of radiology practice in an institution the collective data of all radiological procedures by the investigator and the institution will be collected for the recruitment period. This will help understand what proportion of CE-MR procedures are performed by the investigator and institution.

A qualitative analysis will be performed describing the referral pattern and challenges in a radiological practice.

In addition, as a secondary objective, the study will look at the effectiveness reported as quality of images, diagnostic confidence and customer satisfaction reported on a Likert scale by the local radiologist/technician and spontaneously reported immediate and delayed AEs to assess the effectiveness and safety profile of GBCAs in clinical practice respectively.

During the study, the images will be collected and archived for the initial 50 cases from each investigation centre to be analysed separately at a later stage by a panel of 3 expert MR radiologists. The images will be assessed for the quality of images on the same scale as assessed by the local radiologist. The aim of this second, separate statistical analysis will be to assess the quality of images and see the inter-observer agreement by the expert MR radiologist and assess the agreement in quality of images between real-world reporting by the local radiologist and MR experts' assessment. This analysis will not be part of initial read out of the study due to lack of funding and will be performed at a later date. The current study will be an opportunity to collect and archive the images.

This study's safety monitoring plan is justifiable and adequate from a safety standpoint in view of the following:

- The design of the safety plan permits collection and comparison of the safety response to GBCAs in real life setting based on AEs reported voluntarily by the patient to the physician.
- Consideration of a 7-day documentation of AEs permits the evaluation of late-appearing adverse effects that may emerge or progress after the administration of GBCAs. In line with post-marketing requirements, the investigator will notify sponsor or regulatory authority of AEs he or she becomes aware of after the 7-day documentation interval.

- The measures used to assess effectiveness and safety are well-defined and reliable, and the proposed safety analyses are adequate to assess the effects of the administration of GBCAs.

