9.2 Post-Imaging Period

Safety measurements will be performed from GBCA administration until 7 days post-administration for AEs reported voluntarily by the patient. No follow-up safety assessment is required unless AEs are reported spontaneously by the patient or healthcare providers. However, AEs will be documented in line with the requirements applicable for use of medicines in general, irrespective of the documentation window.

The following information will be collected once at the end of the study:

- Customer satisfaction to be recorded by the local nurse/radiology technician once per centre for each GBCA used at the study centre, including generics
- Investigator information - cumulative numbers for the recruitment period (date of the first patient to date of last patient at the centre) of the study at the centre
- Centre information- cumulative numbers for the recruitment period (date of the first patient to date of last patient at the centre) of the study at the centre

The first 25 consecutive patients where Clariscan is used and the first 25 consecutive patients where any other GBCAs (all together 25 patients) is used, the images will be transferred for storage to allow a blinded image read by the expert MR radiology panel to be performed in a future analysis. If the recruitment is less than 25 for either group, then the total images done for the group (Clariscan or GBCAs) during the recruitment period will be transferred. If a patient has repeat imaging for technical reasons and the image is not readable and has been repeated for same indication/reason, then the second readable image will be transferred for storage and future analysis.

See Section 10.3 and the Study Schedule of Events Table ([Table 2](#)) for further details.

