10.3 Safety Assessments

Clariscan and any other GBCA used in this observational study are approved. Safety data will be collected, assessed and reported in accordance with post-marketing requirements. Clinical trial safety requirements do not apply.

[figure not shown]
The investigator(s) and the sponsor will review the safety data. The following safety data will be collected and evaluated:

AE collection for spontaneously reported AEs and serious AEs (SAEs) will begin at the time of contrast medium injected and continue up to 7 days after GBCA use for individual patient, unless consent is withdrawn. AEs reported in the first hour post-administration will be recorded as “immediate” and any AEs reported after 1 hour and up to 7 days will be recorded as “delayed”. Definition and examples of mild moderate and severe are mentioned in Section 15.2.

All AEs will be tabulated as number reported and percentage:

- 1 AEs, SAEs, severity of AEs, Clariscan vs GBCAs
- 2 AEs, SAEs, severity of AEs, Clariscan vs individual GBCA

Figure 4 Safety Profile

The radiological definition of ‘immediate’ and ‘delayed’ AEs and severity of AEs are in Section 15.2.

AE Definition: An AE is defined as any untoward medical occurrence in a patient or clinical investigation subject administered a pharmaceutical product and which does not necessarily have to have a causal relationship with this treatment. An AE can therefore be any unfavourable and unintended sign (including an abnormal laboratory finding), symptom, or disease temporally associated with the use of a study drug, whether or not considered related to that product. Only symptoms/signs that begin or worsen in severity and/or frequency after GBCA administration/use will be recorded as AEs in the eCRF.

The subjects will be closely observed and questioned with non-leading questioning (e.g., “How do you feel?”). The subjects will be instructed to immediately report any symptoms and signs to the study staff (i.e., between formal observations).

Both the investigator(s) and sponsor/CRO will perform a causality assessment on any AE, to assess whether or not there is a reasonable possibility (evidence to suggest) that the GBCAs caused the event.

Adverse Reaction: An AE that is caused by the GBCA.

Suspected Adverse Reaction: A reasonable possibility exists for causality between the GBCA and the AE.

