12.2 Populations for Analysis

Full Analysis Set

The Full Analysis Set will include all enrolled patients who signed the informed consent.

Effectiveness Analysis Set

The Effectiveness Analysis Set will include all patients who received a GBCA and underwent an MR examination.

Safety Analysis Set

The Safety Analysis Set will consist of all patients who received GBCA during the study.

Investigator Analysis Set

The Investigator Analysis Set will include all investigators who performed at least one GBCA-enhanced MR procedure as part of this study.

Centre Analysis Set

The Centre Analysis Set will include all centres that were approved and initiated to take part in this study and performed at least one GBCA-enhanced MR procedure as part of this study.

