12.7 Safety Variables and Analyses

12.7.1.1 Adverse Events

AEs will be summarised for all GBCAs pooled, for non-Clariscan GBCAs pooled, and for all individual GBCAs administered during the study, including Clariscan. AEs and SAEs will be coded using Medical Dictionary for Regulatory Activities (MedDRA) and all reported events will be listed for the Safety Analysis Set. Immediate treatment-emergent AEs (TEAE) are defined as AEs that occur from the time of treatment administration through 1 hour after administration. Delayed TEAEs are defined as AEs that occur later than 1 hour post-administration up to 7 days post-administration.

The number and percentage of patients with 1 or more AEs will be summarised by system organ class and preferred term. Summaries will also be presented by AE intensity and judged relationship to study drug. Treatment-emergent SAEs will be presented by treatment group for the safety population.

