15.2 Radiological Definitions and Classification of Adverse Events

Reference: [\[ESUR Guidelines 2017\]](#)

ACUTE ADVERSE REACTIONS

Definition: An adverse reaction which occurs within 1 hour of contrast medium injection.

The same acute adverse reactions are seen after iodine- and gadolinium-based contrast agents and after ultrasound contrast agents. The incidence is highest after iodine-based contrast agents and lowest after ultrasound agents.

Classification

Acute reactions are either allergy-like, hypersensitivity reactions or chemotoxic responses. Allergy-like reactions may or may not be true IgE-mediated allergy.

	Allergy-like/ Hypersensitivity	Chemotoxic
Mild	Mild urticaria Mild itching Erythema	Nausea/mild vomiting Warmth/chills Anxiety Vasovagal reaction which resolves spontaneously
Moderate	Marked urticaria Mild bronchospasm Facial/laryngeal oedema Vomiting	Severe vomiting Vasovagal attack
Severe	Hypotensive shock Respiratory arrest Cardiac arrest	Arrhythmia Convulsion

Note:

- Not all symptoms experienced by patients in the hour after contrast medium injection are adverse reactions to the contrast agent.
- Patient anxiety may cause symptoms after contrast medium administration (Lalli effect).
- When a new contrast medium is first introduced, adverse effects tend to be over-reported (Weber effect).

A.1.4. RECORDING ACUTE ADVERSE REACTIONS

- Acute adverse reactions must be properly documented in the patient's records, so that appropriate precautions can be taken before any future examination.
- All reactions requiring medical treatment should be recorded.
- Mild symptoms after contrast medium not requiring treatment should not be recorded. They may be unrelated to the contrast medium and caused by anxiety or by the patient's disease. If such minor symptoms are recorded, the patient may in future be denied a clinically important enhanced examination.
- Full documentation of acute allergy-like reactions includes (a) measuring serum tryptase, preferably immediately after and 2 hours after the reaction, and (b) skin testing one month after the reaction to check for evidence of true allergy to the triggering contrast agent and for evidence of cross-reactivity to other agents.

LATE ADVERSE REACTIONS

Definition:	A late adverse reaction to intravascular iodine-based contrast medium is defined as a reaction which occurs 1 hour to 1 week after contrast medium injection.

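### Delayed adverse events are known only from spontaneous reports, yet their percentages use all dosed patients and are set out by agent, so the Section 6.2 claims of comparison and adequacy are not supported for them

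*Protocol*

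**What the plan says.** **Collection.** Section 6.1: "Patients enrolled in the study will not be actively followed up to collect adverse events (AEs) or outcomes". Section 9.2: "No follow-up safety assessment is required unless AEs are reported spontaneously by the patient or healthcare providers". Section 10.3 applies spontaneous collection from injection to 7 days.

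**Delayed window.** Section 12.7.1.1: "Delayed TEAEs are defined as AEs that occur later than 1 hour post-administration up to 7 days post-administration".

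**Denominator and summary.** Section 12.2: "The Safety Analysis Set will consist of all patients who received GBCA during the study". Section 12.7.1.1: "The number and percentage of patients with 1 or more AEs will be summarised by system organ class and preferred term".

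**Comparison.** Section 10.3 and the synopsis list tables, as number and percentage, of "AEs, SAEs, severity of AEs, Clariscan vs GBCAs", with a second line for Clariscan against each individual agent.

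**Claims.** Section 6.2 says "The design of the safety plan permits collection and comparison of the safety response to GBCAs in real life setting", and adds in that sentence that the events are those patients report voluntarily. It goes on to say that the 7-day window allows late-appearing effects to be evaluated and that the safety analyses are adequate for assessing the effects of giving GBCAs.

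**Text that pulls the other way.** Section 10.3 also says subjects will be closely observed and asked non-leading questions, and Table 2 marks AEs/SAEs at Day 7. Neither describes a contact after imaging.

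**Reporting by newness of agent.** Section 15.2, under acute reactions: "When a new contrast medium is first introduced, adverse effects tend to be over-reported (Weber effect".

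**The concern.** A percentage of patients with an event is an incidence only if event status is known for the patients in the denominator. Here, status after the patient leaves is known only when somebody reports. Silence can mean no event, or an event that nobody mentioned, and the all-dosed denominator treats both as no event.

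The percentages are then laid side by side for Clariscan and the other agents. Treatment is open (Section 8.4), so whoever reports may know which agent was given. The table cannot separate a difference in reactions from a difference in the tendency to report. The secondary objective includes the safety profile of GBCAs, and Section 6.2 tells the reader that this design can support a comparison.

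**Working it through.** **Step 1: the protocol's own figures.** The protocol gives no adverse event rate, reporting rate or safety effect size, so there is no safety figure to reproduce. The only related number is the maximum enrolment of 5,400 (Section 12.9). The caps in Table 1 sum to 200 + 900 + 1,200 + 1,000 + 300 + 900 + 250 = 4,750, which is 650 fewer. That mismatch is a separate matter and the argument does not depend on it. The illustration uses 4,750 with an assumed even split, so 2,375 per group.

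**Step 2: follow one patient through the rules.** The patient is dosed, so enters the Safety Analysis Set (12.2). The patient leaves, and no assessment is required unless a report arrives (9.2). If none arrives, no record is created. Section 12.10 treats missing values as missing, but an absent report is not entered as a missing value, so that rule does not apply. The patient stays in the denominator and adds nothing to the numerator.

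**Step 3: what the percentage estimates.** Let π be the true risk of a delayed event and r the probability that an event is reported.

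- Observed percentage = π × r
- Observed ratio, Clariscan (C) to others (O) = (π_C / π_O) × (r_C / r_O)

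If π_C = π_O, the observed ratio is r_C / r_O, whatever π or the sample size. The bias can also hide a difference: a true ratio of 2 with r_C / r_O = 0.5 shows as 1.0.

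**Step 4: illustration.** All rates here are assumptions. True delayed risk is 2% in both groups, so 0.02 × 2,375 = 47.5 true events per group. z = (p_C − p_O) / √[p_C(1 − p_C)/2,375 + p_O(1 − p_O)/2,375].

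| r_C | r_O | Observed C | Observed O | Ratio | z |
|---|---|---|---|---|---|
| 20% | 20% | 0.4% | 0.4% | 1.0 | 0 |
| 30% | 20% | 0.6% | 0.4% | 1.5 | 0.98 |
| 40% | 20% | 0.8% | 0.4% | 2.0 | 1.79 |
| 20% | 10% | 0.4% | 0.2% | 2.0 | 1.26 |
| 50% | 25% | 1.0% | 0.5% | 2.0 | 2.00 |

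In the first row the ratio is right, but each percentage is one fifth of the true risk. With 40% against 20%, true risks of 1%, 2% and 5% all give a ratio of 2.0, and the chance of a nominal two-sided p below 0.05 is about 24%, 43% and 81%. With 30% against 20% the chances are about 10%, 16% and 34%. No safety test is planned, so the z values and chances only indicate how large the artefact could look.

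**Step 5: are immediate events free of this?** Not on the text. Section 6.2 describes both immediate and delayed events as spontaneously reported, and 10.3 starts spontaneous collection at injection. Nothing says patients stay at the centre for the full hour. Section 15.2 also says that mild acute symptoms needing no treatment should not be recorded, which fits poorly with recording all events. The questioning described in 10.3 may help on site, so the problem is clearest for delayed events, but immediate events need a caveat too.

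**The case against.** **The limit is disclosed.** Section 6.2 names voluntary reporting in the very sentence that claims comparison, several other sections repeat it, and 10.3 says post-marketing rather than clinical trial safety requirements apply. This stands: nothing is concealed, and spontaneous reporting is a legitimate choice for an observational study. The fault lies in the claims drawn from it and in the denominator.

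**Table layout belongs to the analysis plan.** A reader might infer that the two onset windows will be shown only combined. The protocol does not say so: 12.7.1.1 defines them separately just before the summary sentence, and a split may be planned elsewhere. But the 6.2 claims, the 12.2 denominator and the 10.3 comparison are fixed in the protocol itself.

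**There is text on active questioning.** A reader might infer that nearly every patient goes unassessed for delayed events. That is not established: no reporting rate is given, and the questioning in 10.3 and the Day 7 mark in Table 2 point the other way. Neither describes a contact after imaging, and both conflict with 6.1 and 9.2. This is a contradiction to resolve, not an answer to the point.

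**The note on new agents.** A reader might infer that Clariscan's rate will be inflated. The note stands under acute reactions, gives no size, and does not say whether it covers a new product of an existing agent, which Clariscan is (gadoteric acid). It justifies a caveat, not a predicted direction. The delayed-event problem does not rest on it.

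**The remedy changes labels, not numbers.** Partly true: reports per number exposed is the same fraction. What changes is what the fraction is called and what may be concluded from it.

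**Conclusion.** The point holds for delayed adverse events. Percentages over all dosed patients are spontaneous report rates, not incidences, and a difference between Clariscan and other GBCAs cannot be attributed to risk. The Section 6.2 statements on comparison, late-appearing effects and adequacy are not supported for these events.

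The size is unknown because the protocol gives no reporting rate. The relation in Step 3 follows from the collection rule and the denominator. The ratios of 1.5 and 2.0 rest on assumed reporting probabilities, and the percentages and z values also on an assumed true risk and an even split of 4,750 patients. The consequence is confined to a descriptive secondary objective, but correction costs little and should be made.

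**What to change.** 1. In 12.7, and in the matching lines of the synopsis and 10.3, tabulate immediate and delayed events separately.
2. Label delayed events as patients with a spontaneous report per number exposed, state that these are not incidences, and draw no comparative conclusion between Clariscan and other GBCAs from them.
3. Give immediate events by agent descriptively, with a reporting-bias caveat that cites the Weber note in 15.2 and says that the note does not settle whether it covers a new product of an existing agent.
4. Narrow the 6.2 statements on comparison, late-appearing effects and adequacy to match.
5. Reconcile the questioning text in 10.3 and the Day 7 mark in Table 2 with the statements in 6.1 and 9.2 that there is no active follow-up.

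The synopsis and 10.3 need editing along with 12.7 and 6.2, because the comparison lines stand there and would otherwise contradict the new text. The cost is table layout, wording and a narrower safety claim, with no added data collection or patient contact.
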